## List of abbreviations

AE	adverse event
Alk Phos	alkaline phosphatase
ALT (SGPT)	alanine aminotransferase
ANC	absolute neutrophil count
ANCOVA	analysis of covariance
AST (SGOT)	aspartate aminotransferase
ATG	antithymocyte globulin
BID	twice a day
BKV	BK Virus: virus isolated from renal transplant patient, initials B.K.
BPAR	biopsy proven acute rejection
CC	creatinine clearance
CDC	complement dependent cytotoxicity
CI	confidence interval
CIT	cold ischemic time
CKD	chronic kidney disease
CMV	cytomegalovirus
CNI	calcineurin inhibitor
CRF	Case Report/Record Form
CSR	Clinical Study Report
DGF	delayed graft function
DSA	donor-specific antibodies
EC	Ethics Committee
ECG	Electrocardiogram
CRF	electronic Case Report/Record Form
ELISA	enzyme linked immunosorbent assay
ERL	Everolimus
GFR	glomerular filtration rate
ICH	International Conference on Harmonization of Technical Requirements for Registration of Pharmaceuticals for Human Use
IEC	Independent Ethics Committee
IMS	Integrated Medical Safety
IN	Investigator Notification
i.v.	intravenous(ly)
IRB	Institutional Review Board
KDPI	Kidney Donor Profile Index
LLN	lower limit of normal
MDRD	modification of diet in renal disease
MMF	Mycophenolate mofetil
MPA	Mycophenolic acid
NG	nasogastric
OPTN/SRTR	Organ Procurement and Transplantation Network/Scientific Registry of Transplant Recipients
PCR	polymerase chain reaction

p.o.	oral(ly)
QD	once a day
REB	Research Ethics Board
SAE	serious adverse event
SF-36	Medical Outcomes Trust Short Form 36 Health Survey
SOC	Standard of Care
SUSAR	Serious, unexpected, serious adverse reaction
TAC	Tacrolimus
ULN	upper limit of normal
MGTI	MedStar Georgetown Transplant Institute
WBC	white blood cells
WHO	World Health Organization

## Protocol synopsis

**Title of study:** A Pilot Study Comparing the Safety and Efficacy of Zortress (Everolimus) With Low Dose Tacrolimus to Early Conversion to Calcineulin Inhibitor-Free Regimen and Mycophenolic acid With Standard Dose Tacrolimus in Recipients of elevated KDPI and DCD Kidneys

**Purpose and rationale:** The purpose of this pilot study is to evaluate the efficacy and safety of everolimus (1.5 mg/day) with standard therapy in recipients of DCD and kidneys from donors with Kidney Donor Profile Indices greater than 70 .

### Objectives:

- The primary objective of the study is to evaluate efficacy of Everolimus treatment arms compared to Mycophenolate treatment arm with respect to the composite efficacy failure rate including treated Biopsy-Proven Acute Rejection (BPAR) episodes, delayed graft function, graft loss, and death or loss to follow-up. The efficacy will be assessed at 6, 12 and 24 months in recipients of DCD and KDPI kidneys.
- Secondary: To compare renal function (glomerular filtration rate calculated using the MDRD formula) of everolimus with low dose tacrolimus regimen to that of MMF/MPA with standard dose tacrolimus regimen at 24 months post-transplant. Other secondary objectives are: to compare the incidence of CMV and BKV, new onset diabetes mellitus, chronic kidney disease with associated proteinuria, adverse events, serious adverse events and tacrolimus associated adverse events.

### Population:

The study population will consist of a representative group of male and female transplant recipients of DCD and elevated KDPI kidneys, 18-65 years of age undergoing renal transplantation. Approximately 50 patients are planned to be enrolled at MGTI.

### Inclusion/Exclusion criteria:

#### Inclusion criteria

- Male or female recipients 18-65 years of age undergoing primary or secondary kidney transplantation
- Recipients of primary or secondary cadaveric, DCD or elevated KDPI kidneys (defined as follows)
  - Donor whose heart has irreversibly stopped beating, previously referred to as non-heart-beating or asystolic donation
  - Donors whose KDPI is calculated at 70% or greater
- Patients who have given written informed consent to participate in the study

## Exclusion criteria

- Cold ischemic time (CIT) > 30 hours
- ABO incompatible transplants, or T, or B cell crossmatch positive transplant
- Patients with a known hypersensitivity to any of the study drugs or to drugs of similar chemical classes
- Non-controlled DCD
- Donor age >70
- Patients with BMI >35 at baseline before surgery
- Pregnant or lactating females
- Females of childbearing potential unwilling to use an effective means of contraception or are planning to become pregnant
- Patients with platelet count <100,000/mm^3 at the evaluation before randomization.
- Patients with an absolute neutrophil count of < 1,500/mm^3 at baseline before surgery or white blood cell count of < 4,500/mm^3
- Patients who are recipients of multiple solid organ transplants
- Patients who have severe hypercholesterolemia (>350 mg/dL) or hypertriglyceridemia (>500 mg/dL). Patients with controlled hyperlipidemia are acceptable
- Patients who have an abnormal liver profile such as ALT, AST, Alk Phos or total bilirubin >3 times the upper normal limit
- Patients who are treated with drugs that are strong inducers or inhibitors of cytochrome P450 3A4, such as terfenadine, astemizole, cisapride, erythromycin, azithromycin, itraconazole, rifampin or lovastatin
- Patients who received an investigational drug or who have been treated with a non-protocol immunosuppressive drug or treatment within 30 days or 5 half-lives prior to randomization
- Patients with a history of malignancy of any organ system, treated or untreated, within the past 2 years whether or not there is evidence of local recurrence or metastases, with the exception of localized basal cell carcinoma of the skin
- Patients who are HIV positive or Hepatitis C (PCR+ only) or Hepatitis B surface antigen positive
- Recipients of organs from donors who test positive for Hepatitis B surface antigen or Hepatitis C (PCR+ only)
- Patients with a history of severe diarrhea, active peptic ulcer disease, or uncontrolled diabetes mellitus (Hgb A1c <7.0 %) at baseline
- Patients who have any surgical or medical condition, which in the opinion of the investigator, might significantly alter the absorption, distribution, metabolism and excretion of study medication, and/or the presence of severe diarrhea or active peptic ulcer
- Patients who have cardiac failure (e.g. resting dyspnea, symptoms with less than ordinary activity, marked limitation of activity) at time of screening or any other severe cardiac disease as determined by the investigator
- Patients with abnormal physical or laboratory findings of clinical significance within 3 months of randomization which would interfere with the objectives of the study

- Patients with any history of coagulopathy or medical condition requiring long-term anticoagulation therapy after transplantation (Low dose aspirin treatment is allowed)
- Patients with known history of focal segmental glomerulosclerosis
- Presence of psychiatric illness (i.e., schizophrenia, bipolar, major depression) that, in the opinion of the investigator, would interfere with study requirements

#### **Investigational and reference therapy:**

The following pharmaceutical agents will be utilized:

Investigational drug: Everolimus will be provided by Novartis as 0.5 and 0.75 mg tablets.

Control drug: Either MMF or MPA will be administered. For this study, either MMF 1,000 mg BID or MPA 720 mg BID will be allowed since MMF and MPA are considered to be therapeutically equivalent.

Investigational or control drug will be administered as a dual immunosuppressive regimen with tacrolimus initially.

All patients will receive induction therapy, Campath or Simulect. Steroids will be administered and withdrawn according to our institutional practice.

#### **Study Design:**

After obtaining informed consents, patients will be screened for eligibility and randomized within 24h post-transplantation to receive either 1.5 mg of everolimus, 1.5 mg everolimus with CNI-free regimen conversion at month 3, or 1g/720mg of MMF/MPA (1:1:1) in combination with tacrolimus and corticosteroids.

#### **Antibody Induction Therapy:**

Campath (Alemtuzumab) 30 mg or Simulect (basiliximab) 20 mg will be administered at induction of anesthesia along with Solumedrol 500 mg intravenously.

#### **Everolimus treatment arm 1:**

Therapeutic drug monitoring of everolimus and tacrolimus is mandatory throughout the study. From Day 5 on, the everolimus 0.75 mg BID dose will be increased if the trough level is < 3 ng/mL, or reduced if the trough level is > 8 ng/mL. Tacrolimus will be initiated at 0.1 mg/kg/day and adjusted according to our standard practice to achieve target trough levels. From Day 3 on, a whole blood trough concentration will be targeted for 4 to 7 ng/mL. From Month 3, the target tacrolimus trough level will be 2 ng/mL to 5 ng/mL.

#### **Everolimus treatment arm 2:**

Therapeutic drug monitoring of everolimus and tacrolimus is mandatory throughout the study. From Day 5 on, the everolimus 0.75 mg BID dose will be increased if the trough level is < 3 ng/mL, or reduced if the trough level is > 8 ng/mL. Tacrolimus will be initiated at 0.1 mg/kg/day and adjusted according to our standard practice to achieve target trough levels. From Day 3 on, a whole blood trough concentration will be targeted for 4 to 7 ng/mL. From Month 3 (+/- 2 weeks), tacrolimus will be withdrawn and MMF/MPA will be initiated.

### **MMF/MPA treatment arm 3 (SOC):**

MMF/MPA dose will be initiated as 1 g BID (2 g/day)/720 mg BID (1,440 mg/day). Adjustments should be made for adverse events including but not limited to gastrointestinal intolerance and a decrease in WBC. The tacrolimus will be initiated and adjusted to achieve a target whole blood trough concentration of 8 ng/mL to 12 ng/mL. From Month 12 on, the target tacrolimus trough level will be decreased to 6 ng/mL to 8 ng/mL. Steroids will be administered according to our standard practice.

### **Efficacy assessments:**

- Composite efficacy failure rate (treated BPAR, graft loss, death or loss to follow-up)
- Incidence of graft loss, death, or loss to follow-up
- Calculated GFR (eGFR) using the abbreviated MDRD formula

### **Other assessments:**

- Laboratory evaluations of kidney function (including serum creatinine)
- CMV and BKV events
- Glucose intolerance
- Everolimus trough blood levels
- Tacrolimus trough blood levels
- Association with proteinuria
- Vital signs
- Infections and Adverse events
- Serious adverse events
- SF-36 Health Survey questionnaires

### **Statistical analysis:**

All data will be analyzed using the intent-to-treat approach as well as on-treatment based approach. Comparisons between treatment groups experiencing composite efficacy failure and each component will be analyzed with Fisher's exact test. The Chi-square and/or one-way analysis of variance (ANOVA) will be used for acute rejection episodes and creatinine levels respectively.

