## 7 Visit schedule and assessments

Table 7-1 lists all of the assessments and indicates with an “x” the visits when they are performed.

Patients should be encouraged to attend all visits on the designated day. However visit windows will be allowed of  $\pm$  1 day for Days 5 and 7,  $\pm$  3 days for Days 14, 21, and 28 visits,  $\pm$  1 week for Months 2 – 12 visits, and  $\pm$  2 weeks for Months 15 – 24 visits.

Patients who discontinue study drug before completing the study, and those who prematurely withdraw from the study for any reason, should be scheduled for a visit as soon as possible, at which time all of the assessments listed for the final visit will be performed.

Patients who discontinue study drug should also return for the assessments indicated in Table 7-1, including a blood sample for serum creatinine. If they refuse to return for these assessments or are unable to do so, every effort should be made to contact them or a knowledgeable informant by telephone when they refuse to return, and at 6, 12, and 24 months to determine the information on survival status, graft loss/re-transplant, rejection episodes, malignancies, opportunistic infections and immunosuppressive therapies. Since patients will be followed even after discontinuation of study medication, the Study Completion CRF page should only be completed at Month 24 or earlier if the patient can no longer be followed, e.g. death, lost to follow-up, or withdrawal of consent.

All patients will be contacted 30 days after the last dose of study medication regarding Serious Adverse Event information. Graft loss, death and malignancy are considered to be SAEs and should be entered on a SAE form and reported to the relevant regulatory authorities during the follow-up period (beyond 30 days after the last dose). Other Serious Adverse Events that are related to study medication as assessed by the investigator should also be entered on a SAE form and reported to the relevant regulatory authorities during the follow-up period.

Patients who prematurely discontinue study medication due to death, lost to follow up or patient withdrew consent will not have any post-study follow up evaluations.

At a minimum, patients will be contacted for safety evaluations during the 30 days following the last dose of study drug or last completed visit (whichever is later), including final contact at the 30-day point. Documentation of attempts to contact the patient should be recorded in the patient record.

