#### **7.4.4 Graft Loss**

The allograft will be presumed to be lost on the day the patient starts dialysis and is not able to subsequently be removed from dialysis. If the patient undergoes a graft nephrectomy, then the day of nephrectomy is the day of graft loss. This will be reported on the premature discontinuation of study medication CRF, if medication is discontinued prematurely. The reason for graft loss will be recorded on the Graft Loss CRF. If graft loss occurs after the patient has discontinued study medication, the appropriate Follow-Up CRF should be completed. Graft loss is considered a Serious Adverse Event and should be reported on the Serious Adverse Event CRF and the SAE form must be reported to the relevant regulatory authorities within 24 hours.

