### **Premature study discontinuation and follow-up**

For all patients prematurely discontinuing study medication, a post-study follow-up contact will be made at 6, 12, and 24 months after transplantation, except in patients who prematurely discontinue study medication due to death, lost to follow up or patient withdrew consent. Information on allograft and patient survival, malignancies, rejection episodes, and current immunosuppressive regimen will be collected. A blood sample will also be collected for serum creatinine. All patients will be contacted 30 days after the last dose of study medication regarding Serious Adverse Event information. Graft loss, death and malignancy are Serious Adverse Events and should be entered on a SAE form and

reported to the relevant authorities during the follow-up period (beyond 30 days after the last dose). Other Serious Adverse Events that are related to study medication as assessed by the investigator should also be entered on a SAE form and reported to the IRB and other relevant authorities during the follow-up period.

Clinically notable laboratory abnormalities present at the time of discontinuation will be followed until the abnormality is no longer considered clinically significant.

This will be captured on the Study Completion CRF. Reason must be provided.

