#### **10.4.3 Handling of missing values/censoring/discontinuations**

All efforts will be made to complete data except for cases of loss to follow-up, graft loss or death. Loss to follow-up, graft loss or death is defined as one whose last day of contact is prior to Month 24 and who did not experience graft loss or death. The missing data will be assumed to be missing at random except for above cases. The sensitivity analysis based on a complete case analysis and a missing data analysis will be conducted if imputed data exceeds 5 % of total data.

The modified last observation carried forward (LOCF) will be applied if eGFR has not been obtained at study visits. Only in cases where the observed measurement was obtained within 6 weeks of the expected study visit, modified LOCF will be employed to impute missing data. In other words, missing data will be replaced with data from out-of-window visit occur within 6 weeks of scheduled visit. None of data will be carried forward beyond 6 weeks, and will not be imputed by other methods. For the FAS analysis, this will be done regardless of whether a patient discontinued study medication or not. For patients experiencing graft loss, the last value before dialysis or re-transplantation will be used.

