#### **10.5.3 Health-related Quality of Life (HQOL)**

The SF-36 will be employed to assess HQOL in study subjects at Day 7, 28, Month 6, 12 and 24 post-operation. The mean scores of SF-36 will be summarized by visits according to treatment group. The change from baseline in the summary scores will be compared using an ANOVA with treatment as a factor. If the assumptions of the model are not met, the analysis will be done using Kruskal-Wallis tests.

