#### **10.7 Power for analysis of critical secondary variables**

Correlation between laboratories will be checked periodically throughout the study period. eGFR will be calculated using MDRD formula for each visit following the kidney transplantation. All data will be analyzed using the intent-to-treat approach as well as on-treatment based approach. Comparisons between treatment groups experiencing composite efficacy failure and each component will be analyzed with Fisher's exact test. The Chi-square and/or one-way analysis of variance (ANOVA) will be used for acute rejection episodes and creatinine levels respectively.

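### The supplementary serum-creatinine ANOVA has no graft-loss rule and no rank fallback, so dialysis values can enter it and cost power

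*Combined protocol and SAP*

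**What the plan says.** **The test.** The synopsis (Statistical analysis) and section 10.7 carry the same sentence: "The Chi-square and/or one-way analysis of variance (ANOVA) will be used for acute rejection episodes and creatinine levels respectively". Section 10.7 adds: "All data will be analyzed using the intent-to-treat approach as well as on-treatment based approach". Neither place gives a scale, a visit or a rule for patients who have lost the graft.

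**Sampling after study drug stops.** Section 7 says: "Patients who discontinue study drug should also return for the assessments indicated in Table 7-1, including a blood sample for serum creatinine". The text on premature study discontinuation under section 7.5 sets contacts at 6, 12 and 24 months and says: "A blood sample will also be collected for serum creatinine". Section 6.5.8 lists serum creatinine and graft loss or re-transplant together among the items collected in follow-up. The exceptions are narrow. Patients who stop study medication "due to death, lost to follow up or patient withdrew consent will not have any post-study follow up evaluations". Graft loss is not among them.

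**What graft loss means.** Section 7.4.4: "The allograft will be presumed to be lost on the day the patient starts dialysis", provided the patient cannot later come off dialysis. Graft nephrectomy also counts.

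**The graft-loss rule.** The second paragraph of section 10.4.3 opens: "The modified last observation carried forward (LOCF) will be applied if eGFR has not been obtained at study visits". It ends by substituting the last value before dialysis or re-transplantation. Creatinine is not named.

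**Comparable variables.** Section 10.5.2 uses a Wilcoxon rank-sum test for the urine protein/creatinine ratio. For SF-36, section 10.5.3 says: "If the assumptions of the model are not met, the analysis will be done using Kruskal-Wallis tests". Creatinine has neither provision.

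**The concern.** A creatinine value taken on maintenance dialysis describes the dialysis, not the graft, and it lies far above the values of patients with working grafts. With 16 patients per arm, one such value moves the arm mean and inflates the ANOVA error variance. A real difference among the remaining patients can then go undetected, and the reported mean can describe one patient more than the arm. Creatinine is named as a renal-function measure in section 7.4.6, so readers of the pilot are likely to look at it. The trial recruits recipients of DCD or KDPI 70 or greater kidneys, and graft loss is a component of its primary composite, so the plan itself provides for graft losses.

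**Working it through.** **Inputs from the documents.** Three arms of 16 (section 10.6), one-way ANOVA, creatinine sampling continued after study drug stops. The plan states no power or effect size for creatinine, so there is no figure to reproduce.

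**Assumptions, none of them in the documents.** Creatinine level and spread, treatment ratio, dialysis values, last pre-dialysis values and graft-loss rate.

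**Step 1: one value in one arm.** Assume fifteen patients with mean 1.6 and SD 0.5 mg/dL and one dialysis value v.
- Shift in arm mean = (v − 1.6)/16. For v = 8: 6.4/16 = 0.40 mg/dL. For v = 5: 3.4/16 = 0.21 mg/dL.
- Arm SD for v = 8: the new mean is 2.0, so the variance is (14 × 0.5² + 15 × 0.4² + 6.0²)/15 = (3.5 + 2.4 + 36)/15 = 2.79, and the SD is 1.67. For v = 5 the same formula gives 0.98.

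One patient thus shifts the mean by 0.4 to 0.8 of the original SD (0.21/0.5 and 0.40/0.5) and raises the SD two- to threefold.

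**Step 2: how often this could arise.** The chance of at least one graft loss among 48 patients is 1 − (1 − p)^48. At an assumed 2% this is 62%, at 5% it is 91%, and at 10% it is 99%.

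**Step 3: power of the three-arm test, by simulation.** Lognormal with median 1.5 mg/dL and CV 40% (log-scale SD = √ln(1 + 0.4²) = 0.385), one arm 1.4 times higher (median 2.1), 16 per arm, two-sided 0.05. Each patient has the stated chance of a dialysis value drawn from 5-10 mg/dL. Simulation error is about one to two points.

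| Assumed dialysis fraction | One-way ANOVA | Kruskal-Wallis |
|---|---|---|
| none | 68% | 67% |
| 2% | 44% | 62% |
| 6.25% (on average 1 in 16) | 21% | 54% |

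At 6.25%, ANOVA on the log scale reaches 41%, so a log transformation recovers part of the loss.

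**Step 4: other ways of handling graft loss, at 6.25%.**
- Last pre-dialysis value carried forward (assumed 3-5 mg/dL): ANOVA 47%, Kruskal-Wallis 56%.
- Patients with graft loss left out: ANOVA 66%, Kruskal-Wallis 63%.
- Patients with graft loss ranked worst: Kruskal-Wallis 54%, the same as ranking the measured values.

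**Step 5: no true difference.** With dialysis values present, ANOVA rejects in about 3-5% of trials, which is no more than nominal.

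**The case against.** **The key renal comparison lies elsewhere.** A reader might infer that the trial's renal-function comparison is compromised. The documents do not support that. Section 3.2 makes calculated GFR the key secondary measure, section 10.5.2 analyses it by ANCOVA with Month 1 GFR and induction therapy, and section 10.4.3 gives it a graft-loss rule. A high creatinine also maps to an eGFR near zero, so its influence is bounded. The synopsis lists serum creatinine under other assessments. This stands, and it confines the point to the creatinine ANOVA.

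**Section 10.4.3 may already cover creatinine.** Its graft-loss sentence does not restrict itself to eGFR in so many words, and eGFR is computed from the same blood sample. It is therefore too strong to say that dialysis values will certainly enter. But the sentence closes a paragraph about eGFR, and nothing extends it to the test in section 10.7. Even on the wide reading, the rank test keeps a 9-point advantage (56% v 47%).

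**The missing rule matters more than the choice of ANOVA.** This largely stands. If patients with graft loss are left out, ANOVA is marginally ahead (66% v 63%). Leaving them out, however, drops the worst outcomes after randomisation and does not fit an intent-to-treat analysis. The additional on-treatment analysis may exclude some of these values, but it does not repair the intent-to-treat one.

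**False positives.** A reader might infer that one patient could create a spurious significant result. The test does not behave that way: the error variance rises with the mean, and rejection under no difference stays at 3-5%. Only the descriptive mean is distorted, and section 10.5.2 also reports medians and ranges, where an outlier would be seen.

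**An unstated scale is not a stated raw scale.** True. The raw scale is inferred from silence, though it is the natural reading of an unqualified ANOVA of creatinine levels.

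**Conclusion.** The point holds for the supplementary creatinine comparison. The plan applies a one-way ANOVA with no stated transformation or rank fallback, continues sampling after graft loss, and has no graft-loss rule that clearly reaches creatinine. The consequence is lost power and a distorted arm mean. Under the assumptions above, ANOVA gives up about 18 points to the rank test at a 2% dialysis fraction (44% v 62%) and about 33 points at 6.25% (21% v 54%). It gives up about 9 points at 6.25% if the section 10.4.3 rule is read to cover creatinine. With no graft loss the two tests are equivalent.

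These sizes rest on a creatinine distribution, treatment ratio, dialysis range and graft-loss rate that the documents do not give. The direction does not depend on the exact figures; the amount does. Because creatinine is a lower-tier variable in a 48-patient pilot and eGFR is unaffected, the priority is minor.

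**What to change.** In the synopsis (Statistical analysis) and section 10.7:

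1. Replace the one-way ANOVA for creatinine with a rank test: Kruskal-Wallis across the three arms, or Wilcoxon for each everolimus arm against MMF/MPA, in line with section 10.5.2 for the urine protein/creatinine ratio.
2. Name the time points. Months 12 and 24 match those set for renal function in section 3.2.
3. State one rule so that values measured on dialysis, or after re-transplantation, are not analysed as function of the study graft. Either rank patients with graft loss worst, or extend the last-pre-dialysis-value rule of section 10.4.3 to creatinine by name.

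The second option in item 3 keeps creatinine consistent with eGFR from the same sample. The first makes the creatinine result partly reflect graft loss, which is already in the primary composite and analysed alone in section 10.5.1; if it is chosen, the report should say so. Reporting creatinine descriptively, with medians and ranges and no test, would also be acceptable.

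The cost is wording only, with no new data or visits, and about 1-2 points of power if no graft is lost.
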